### **5.2.6      Sipuleucel-T Product Failures and Leukapheresis Rescheduling**

In the event that a subject's leukapheresis procedure fails, sipuleucel-T does not meet quality release specifications, or infusion is not possible for any other reason, the subject may be scheduled to undergo a repeat leukapheresis procedure. A minimum of 2 days must have elapsed since the last leukapheresis procedure. Scheduling will depend upon capacity of the leukapheresis and Dendreon manufacturing facilities. If the second or third leukapheresis appointment is delayed or rescheduled for any reason, a physical examination and all other

preleukapheresis procedures must be repeated within the 5 days prior to the next leukapheresis procedure. The preleukapheresis immune monitoring samples will not be drawn again.

There is a possibility that a subject's sipuleucel-T may fail to meet quality requirements more than once. In such instances, the subject may not receive all 3 infusions. In rare instances, it may be determined that it is not possible to manufacture sipuleucel-T that passes quality control (QC) testing from a subject's leukapheresis product.

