### **6.8.2 Sipuleucel-T Lot Release**

Prior to infusion, small samples (3% to 4%) of cellular components from pre and post-culture (PA2024) cells will be used to assess product potency as part of the normal sipuleucel-T manufacturing process.

Sipuleucel-T lot release assessments will include total nucleated cell (TNC) count, CD54+ cell count and CD54 upregulation.

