### **8.5.6.1 Other Analyses**

Use of select anticancer treatments during the study will be summarized by treatment group. This summary will include types of therapies used and will be based on the ITT population.

Data from sipuleucel-T lot release assessments will be summarized. Data to be summarized include CD54 upregulation, CD54+ cell count, and TNC count. These data will be summarized descriptively by infusion (1, 2, and 3) and cumulative (summed across infusions). Cumulative lot release assessment data will be compared between both arms using a t-test on the logarithm scale based on the immune response analysis population.

Prostate specific antigen data, including change from baseline, will be summarized descriptively by treatment arm at each time point for the ITT population. Additionally, the maximal decline of serum PSA from baseline at any time point will be summarized using waterfall plots. Baseline will be defined as the value collected immediately prior to the registration PSA value. Additional analyses of PSA will be performed using the most recent PSA value prior to the initiation of enzalutamide as the baseline value.

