3.2 Analysis Populations

3.2.1 Immune Response

The immune response population will be defined as subjects who receive 3 infusions of sipuleucel-T and 10 or more weeks of enzalutamide. Analysis of immune response endpoints, including the primary endpoint, will be performed using this population. This population will also be used to perform supplementary analyses of nonimmune response efficacy endpoints.

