4.1 Product Characterization

Product parameters to be summarized are: CD54 upregulation, CD54⁺ cell count, and TNC count. Product parameters will be summarized descriptively (n, mean [geometric mean], standard error, median, minimum, and maximum) by Infusion (1, 2, and 3) and cumulative (summed across infusions). Cumulative product parameters will be compared between both arms using a Wilcoxon test based on the immune response population. Cumulative CD54 upregulation is the primary endpoint for the study.

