4.6.8 Study Treatment Administration

To evaluate the sipuleucel-T infusion success and failure rate over the course of the study, the following information will be summarized:

- a) Number of subjects who received a total of 0, 1, 2, or 3 infusions
- b) Number of subjects undergoing leukapheresis for infusions 1, 2, and 3
- d) Number of subjects undergoing leukapheresis more than once for infusions 1, 2, and 3
- e) Number of subjects failing to receive three infusions due to insufficient TNC count and/or CD54 upregulation
- f) Elapsed time between infusions
- g) Elapsed time between randomization and infusion 1

Items a) through e) will be summarized by their frequency distribution and by treatment group. Items f) and g) will be summarized with descriptive statistics (mean, median, standard deviation, minimum, and maximum) by treatment group.

The duration of treatment with enzalutamide will be summarized descriptively by randomized treatment groups. The reasons for stopping enzalutamide will be summarized descriptively by randomized treatment groups.

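### The arm comparison of CD54 upregulation, CD54+ count and TNC uses only infused lots in men with 3 infusions and at least 10 weeks of enzalutamide, so it can attenuate a true product difference

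*SAP*

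**What the plan says.** SAP 4.1 (Product Characterization) summarizes CD54 upregulation, CD54+ cell count and TNC count by infusion and as a sum over infusions. It then states: "Cumulative product parameters will be compared between both arms using a Wilcoxon test based on the immune response population". The same section adds: "Cumulative CD54 upregulation is the primary endpoint for the study".

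SAP 3.2.1 defines that population: "The immune response population will be defined as subjects who receive 3 infusions of sipuleucel-T and 10 or more weeks of enzalutamide". Protocol 8.5.6.1 plans the comparison in the same population with a different test; the cumulative data "will be compared between both arms using a t-test on the logarithm scale".

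Protocol 6.8.2 makes the compared parameters the release measures: "Sipuleucel-T lot release assessments will include total nucleated cell (TNC) count, CD54+ cell count and CD54 upregulation". Under Protocol 5.2.6, a man may have a repeat leukapheresis when the collection fails, when "sipuleucel-T does not meet quality release specifications, or infusion is not possible for any other reason". Appendix 4 forbids infusion without written approval of the lot.

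SAP 4.6.8 reports by arm the infusions received, the men with more than one leukapheresis for an infusion, and the "Number of subjects failing to receive three infusions due to insufficient TNC count and/or CD54 upregulation". The table shells in SAP 5 (14.2.7.1, 14.2.8.1, 14.2.9.1) add by-infusion summaries in men with at least 1 infusion.

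**The concern.** Only the concurrent arm takes enzalutamide while its lots are made. If enzalutamide changes CD54 upregulation or cell yield, it also changes which lots pass release and which men reach 3 infusions. A lot rejected for a low value has no infusion number, so on the natural reading of SAP 4.1 it enters neither the by-infusion summary nor the sum. A man whose lots keep failing leaves the comparison altogether. What remains is a comparison of passing lots among men who had three of them. That differs from the aim in SAP 1, which is the effect of concurrent versus sequential enzalutamide on cumulative CD54 upregulation.

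At stake is a small trial (25 concurrent, 27 sequential) reporting that product quality is similar when part of the difference was removed before the test. Randomization does not protect a comparison selected in this way.

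**Working it through.** **The plan's own figures.** The documents give no sample size, power, variance or failure rate for the product parameters. The only power figures concern PA2024 T cell proliferation, and they reproduce. The log-scale SD is sqrt(ln(1 + 1.25²)) = 0.970 and the difference is ln 2 = 0.693. The noncentral t gives 90.6% power with 43 per arm (stated 90%) and 69.7% with 25 per arm (stated about 70%). The point below does not rest on them.

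**Inputs from the documents.** Three lots per man, a sum over infused lots, infusion only after approval, repeat leukapheresis allowed after a failure, and 25 versus 27 men. Protocol synopsis: a minimum of 50 million APCs per dose. No limit is given for CD54 upregulation or TNC.

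**Assumptions.** Lot values are log-normal with CV 0.3, 0.5 or 1.25 and within-man correlation 0.5. One release cut-off applies to both arms. Sequential-arm lot failure is 2%, 5% or 10%. Each failed lot gets one repeat. The true concurrent/sequential ratio is 0.80.

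**Step 1, one lot, small effect.** For a normal variable cut off below at failure rate p, let α = z(p) and λ = φ(α)/(1 − p). The proportion of the effect lost is λ(λ − α). At p = 5%, α = −1.645 and λ = 0.1031/0.95 = 0.1086, so the loss is 0.1086 × 1.754 = 19%. At 2% it is 10%, and at 10% it is 29%.

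**Step 2, simulation with every failure on the compared measure.** In each cell the three values are for CV 0.3 / 0.5 / 1.25.

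| Sequential lot failure | Concurrent lot failure | Observed ratio (true 0.80) | Men with 3 infusions at CV 0.5, sequential v concurrent |
|---|---|---|---|
| 2% | 9.8% / 5.7% / 3.4% | 0.833 / 0.823 / 0.819 | 99.1% v 96.5% |
| 5% | 18.8% / 12.0% / 7.8% | 0.857 / 0.846 / 0.837 | 96.9% v 90.6% |
| 10% | 30.1% / 20.8% / 14.6% | 0.880 / 0.870 / 0.860 | 92.6% v 81.0% |

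With all first-attempt lots counted, the ratio is 0.80 throughout. With no true effect, the selected ratio stays at 1.00. At CV 0.5, Wilcoxon power is about 51% using all lots, against 46%, 40% and 32% under the planned selection.

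**Step 3, one third of failures on the compared measure, the rest independent of it.** With CV 0.3 to 0.5, within-man correlation 0.3 to 0.6 and up to 5 leukaphereses, the loss of log effect is 5–9%, 11–16% and 18–25% at 2%, 5% and 10% failure. The observed ratio is 0.80^(1 − loss):

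- 2%: 0.80^0.95 = 0.81 to 0.80^0.91 = 0.82
- 5%: 0.80^0.89 = 0.82 to 0.80^0.84 = 0.83
- 10%: 0.80^0.82 = 0.83 to 0.80^0.75 = 0.85

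**Step 4, the 10-week condition.** Concurrent men meet it about 10 − 2 = 8 weeks after first leukapheresis. Sequential men meet it at about week 10 + 10 = 20 after first infusion. Suppose 20% of sequential and 5% of concurrent men are lost, and fitness correlates 0.3 to 0.5 with the product value (CV 0.5). With no product effect, the ratio becomes 0.97 to 0.95. That is away from 1, so it could offset or exceed the attenuation of a harm.

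**The case against.** A reader might infer that the plan certainly understates harm from enzalutamide and hides it. The documents do not support that, for four reasons.

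- **Direction.** With no failures on these measures, or no true effect, the release selection causes no bias. It would shrink a benefit as well as a harm, and Protocol 1.1.1 raises possible synergy. The 10-week half of the same population could push the other way, so the net bias has no known sign.
- **Size.** Protocol 5.2.6 allows for failures unrelated to the measure compared, such as a failed leukapheresis. Attributing every failure to that measure is an upper scenario.
- **Visibility.** SAP 4.6.8 counts failures and repeats by arm, and SAP 5 plans a listing of cell product parameters. An imbalance would be seen.
- **Importance.** The stated primary objective in both documents is T cell proliferation, even though SAP 4.1 calls CD54 upregulation primary. SAP 4 labels all tests descriptive or exploratory.

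These points limit certainty, size and weight, and they stand. They do not restore the comparison: counts beside a p-value leave the estimate unchanged, and the at-least-1-infusion tables still contain infused lots only. That rejected lots are left out is itself inferred from the by-infusion wording, not stated outright.

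**Conclusion.** The concern holds in conditional form. The planned test conditions on passing release on the measures it compares and on completing 3 infusions, and concurrent enzalutamide could affect both. If lots fail on these measures and enzalutamide shifts them, the release and 3-infusion selection attenuates the arm difference.

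For an assumed true ratio of 0.80 and 2% to 10% sequential-arm lot failure, the observed ratio would be about 0.82 to 0.88 in the upper scenario and about 0.81 to 0.85 if one third of failures are on the compared measure. Neither range allows for the 10-week condition. Failure rates, CVs, correlations and the repeat rule are all assumed, so these figures show plausible size and are not estimates for this trial. If few lots failed, the effect is small. The change is worth making but is not critical, because the analyses are exploratory.

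**What to change.** In SAP 4.1:

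1. Make the product-quality comparison in all randomized subjects with at least one leukapheresis, by randomized arm, without the 3-infusion and 10-week conditions. Use the release values of the first manufacturing attempt at each planned leukapheresis, whether or not the lot was released.
2. Report lots without release values by arm and reason. Rank them lowest only when the recorded reason is product failure.
3. Report lot-failure and 3-infusion completion rates by arm beside the comparison.
4. Optionally add a cumulative delivered value, with 0 for each infusion not received, as a separate delivered-dose analysis. Label it as also reflecting withdrawal and progression, since Protocol 4.3.3 lists these among the reasons for stopping treatment.
5. Keep the planned Wilcoxon test as supportive.

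At least one leukapheresis is still a post-randomization condition, because only the concurrent arm has a run-in before it. SAP 4.6.2 already counts these men by arm, so the loss can be shown.

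The cost is SAP wording and a few extra tables. Appendix 4 of the protocol says quality control testing is done on each product, so values should exist for lots that reached testing; the sponsor should confirm that they are in the analysis data. Lots terminated in process will have some missing values.

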## **8.4 Endpoints**

### **8.4.1 Primary Endpoint(s)**

The primary endpoint is peripheral PA2024-specific T cell immune response to sipuleucel-T over time as measured via a T cell stimulation index from a proliferation assay. This endpoint was selected because it has demonstrated the highest signal to noise ratio of all the T cell assays Dendreon has evaluated in prior studies of sipuleucel-T (data on file).

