### **8.5.3 Efficacy Analyses**

The primary efficacy analysis will consist of a repeated measurement analysis of immune response over time evaluated using PA2024-stimulated T cell proliferation via tritiated-thymidine uptake based on the immune response population. The logarithm of response will be used for analysis. Fixed effect terms in the model will include treatment arm, visit as a class effect, and treatment by visit interaction. The correlation of responses across time within a subject will be modeled using several candidate variance-covariance structures including unstructured, compound symmetry, heterogeneous compound symmetry, autoregressive (1), and heterogeneous autoregressive (1). The variance-covariance structure providing the smallest Bayesian information criteria will be selected for the final model. Fixed effect terms in the model will be tested for significance using type III sums of squares. The formal test for difference between the treatment arms will be based on the p-value for the treatment arm effect unless a significant treatment by visit interaction ( $p < 0.05$ ) is observed, in which case by-visit treatment comparisons will be made using appropriate contrast statements. Estimates of treatment effect and corresponding 95% confidence intervals (CIs) will be provided on the ratio scale obtained by exponentiation of the model derived treatment effect and CI on the logarithm scale. Immune responses over time for other assays will be analyzed using identical methods described for the primary efficacy analysis except for the ELISPOT, which will be analyzed using ranks instead of on the logarithm scale.

The response rate for each assay and for each antigen will be compared between treatment arms at each visit using Fisher's exact test based on the immune response population. In addition, analyses will be performed modeling response rates over time using appropriate methods to account for the correlation of responses over time within a subject.

Time to PSA progression will be compared between the treatment arms using a Cox regression model with terms for treatment, baseline PSA (logarithm scale), and baseline LDH (logarithm scale) in the model based on the ITT population. The estimated HR of the treatment effect and

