1 STUDY DESIGN

Protocol P12-2 is a randomized, open-label study designed to examine the effects on cumulative CD54 upregulation of concurrent and sequential administration of enzalutamide administered in combination with sipuleucel-T in mCRPC subjects. All subjects will be scheduled to receive three infusions of sipuleucel-T as well as a total of 52 weeks of therapy with enzalutamide either concurrently with or following administration of sipuleucel-T. This study consists of 3 phases. The screening phase will begin at the completion of the informed consent process and continue through registration. The active phase will begin at registration and continue through the post-treatment visit (30 to 37 days following the last study treatment). The long term follow-up (LTFU) phase will begin after the post-treatment visit and will continue until the subject's death or until Dendreon terminates the study.

Registered subjects will be randomized (1:1) to either the Concurrent Arm or the Sequential Arm. Subjects will be stratified by screening PSA levels (≥ 25 ng/mL, yes or no) and screening lactate dehydrogenase (LDH) levels (≥ 200 IU/L, yes or no), both obtained from the central laboratory.

Enzalutamide treatment will occur either concurrently with sipuleucel-T (concurrent arm), or following administration of sipuleucel-T (sequential arm):

- **Concurrent Arm:** Subjects will receive sipuleucel-T concurrently with enzalutamide (160 mg orally once daily). Enzalutamide treatment will start 2 weeks prior to the first leukapheresis and continue for 52 weeks or until disease progression or unacceptable toxicity, whichever occurs first. Subjects randomized to the concurrent arm who receive the 2-week enzalutamide run-in, but do not subsequently receive at least one partial (> 0 mL) infusion of sipuleucel-T will not receive any additional enzalutamide treatment, will undergo a post-treatment visit, and will enter the LTFU phase.
- **Sequential Arm:** Subjects will receive sipuleucel-T followed by enzalutamide (160 mg orally once daily). Enzalutamide treatment will start approximately 10 weeks after the first infusion of sipuleucel-T and continue for 52 weeks or until disease progression or unacceptable toxicity, whichever occurs first. Subjects randomized to the sequential arm who do not receive at least one partial (> 0 mL) infusion of sipuleucel-T will not receive any enzalutamide treatment, will undergo a post-treatment visit, and will enter the LTFU phase.

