2 STUDY OBJECTIVES

2.1 Primary Study Objective

- To evaluate peripheral PA2024-specific T cell immune response to sipuleucel-T over time via a T cell stimulation index from a proliferation assay.

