3 STATISTICAL CONSIDERATIONS

3.1 Sample Size Considerations

Approximately 100 subjects will be registered and randomized 1:1 to the Concurrent Arm or the Sequential Arm, with 50 subjects per arm.

PA2024-specific T cell proliferation responses over time will be compared between the concurrent arm and sequential arm using a repeated measurement mixed model analysis. With 43 subjects per arm, there is approximately 90% power to detect a 2-fold difference in mean response between the arms at any time point assuming a coefficient of variation of 1.25. To allow for drop-outs and subjects who may not receive 3 infusions of sipuleucel-T or at least 10 weeks of enzalutamide, approximately 50 subjects per arm will be enrolled.

In the fourth quarter of 2013 Dendreon modified the enrollment goals for this study pursuant to a corporate reorganization plan. Planned enrollment was reduced from 100 subjects to the approximately 50 subjects known to have enrolled at the time of this reorganization. Comparing PA2025-specific T cell proliferation responses over time between the concurrent arm and the sequential are with 25 subjects per arm, there is approximately 70% power to detect a 2-fold difference in mean response between the arms at any time point assuming a coefficient of variation of 1.25. A determination was made that no protocol amendment was required and on February 14, 2014, all participating sites were notified of the decision to stop enrolling subjects. Ultimately, 52 subjects were enrolled: 25 in the Concurrent Arm and 27 in the Sequential Arm

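### SAP 4.1 names cumulative CD54 upregulation as the primary endpoint, while the protocol and the rest of the SAP make it the PA2024-specific T cell stimulation index

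*SAP*

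**What the plan says.** **Text pointing to CD54.** SAP 4.1 (Product Characterization) states "Cumulative CD54 upregulation is the primary endpoint for the study". SAP 1 describes the study as "designed to examine the effects on cumulative CD54 upregulation of concurrent and sequential administration of enzalutamide", but does not use the word primary.

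**Text pointing to PA2024 T cell proliferation.** SAP 2.1 gives the primary objective as "To evaluate peripheral PA2024-specific T cell immune response to sipuleucel-T over time via a T cell stimulation index from a proliferation assay", and Protocol 2.1 has the same objective. Protocol 8.4.1 says "The primary endpoint is peripheral PA2024-specific T cell immune response to sipuleucel-T over time" and gives a reason: the best signal-to-noise ratio among the T cell assays the sponsor has evaluated. Protocol 8.5.3 makes the repeated-measures analysis of log PA2024 proliferation the primary efficacy analysis. It adds that "The formal test for difference between the treatment arms will be based on the p-value for the treatment arm effect", unless the treatment-by-visit interaction has p<0.05, when by-visit contrasts are used. SAP 3.1 bases sample size on proliferation: "PA2024-specific T cell proliferation responses over time will be compared between the concurrent arm and sequential arm using a repeated measurement mixed model analysis".

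**Populations.** SAP 3.2.1 defines the immune response population (3 infusions and at least 10 weeks of enzalutamide) and says "Analysis of immune response endpoints, including the primary endpoint, will be performed using this population". SAP 3.2.3 then assigns all immune response variables to the safety population as well.

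**CD54 in the protocol.** Protocol 8.5.6.1, under Other Analyses, treats CD54 upregulation as lot-release data: "Cumulative lot release assessment data will be compared between both arms using a t-test on the logarithm scale". SAP 4.1 uses a Wilcoxon test for the same comparison.

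**The concern.** A plan should name one primary endpoint. Here the SAP contradicts the protocol and also itself. The two candidates differ in kind. CD54 upregulation is measured on the manufactured product at lot release; the stimulation index is measured in the subject's peripheral blood over time. They also lead to different analyses: a two-sample test on a cumulative value, or a mixed model over visits.

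The stake is which result the study report presents as primary. The trial is open-label, and SAP 4.7.1 allows periodic summaries of both product characteristics and immune response. An unsettled label leaves room to pick the headline after data have been seen.

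Correcting the label alone would not be enough. The PA2024 endpoint would still have two analysis populations in the SAP and no named main comparison.

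**Working it through.** **1. The plan's own power figures, to see which endpoint the design serves.** Inputs from SAP 3.1 and Protocol 8.1 and 8.2: 2-fold ratio, coefficient of variation 1.25, two-sided 0.05, one time point.

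- Log-scale SD = sqrt(ln(1 + 1.25²)) = sqrt(ln 2.5625) = 0.970.
- Log-scale difference = ln 2 = 0.693.
- Noncentrality = 0.693 / (0.970 × sqrt(1/n1 + 1/n2)); power from the noncentral t distribution.

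| n per arm | Noncentrality | Power | Stated |
|---|---|---|---|
| 43 and 43 | 3.31 | 90.6% | about 90% |
| 25 and 25 | 2.53 | 69.7% | about 70% |
| 25 and 27 (enrolled) | 2.57 | 71.4% | none |

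Power at 42 per arm is 89.9%, so 43 is the smallest n that reaches 90%. Both stated figures reproduce, and both are for T cell proliferation (the second writes PA2025, evidently a slip). Neither document gives an effect size, coefficient of variation or power for cumulative CD54 upregulation, so power for the endpoint named in SAP 4.1 cannot be computed.

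**2. The passages side by side.**

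| Place | What it supports |
|---|---|
| SAP 4.1 | CD54, explicitly primary |
| SAP 1 | CD54 as the design aim, not called primary |
| Protocol 2.1, SAP 2.1 | PA2024 index, primary objective |
| Protocol 8.4.1 | PA2024 index, primary endpoint |
| Protocol 8.5.3 | PA2024 index, primary analysis |
| SAP 3.1 | PA2024 by implication (both power statements) |
| SAP 3.2.1 | An immune response endpoint, by implication |
| Protocol 8.5.6.1 | CD54 as an other analysis |

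**3. Is a change recorded?** The SAP describes two changes to the study: the enrollment cut, for which no protocol amendment was judged necessary (3.1), and the decision to terminate in 2017 (1). Neither mentions the endpoint.

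**4. What SAP 4.2 gives the PA2024 endpoint.** It specifies a mixed model on the log stimulation index with arm, visit, their interaction and the stratification factors, starting from the baseline sample, with contrasts at specific visits. It does not carry over the Protocol 8.5.3 rule for choosing between the arm effect and by-visit contrasts, so no comparison is identified as the main one. If the arm effect is used with baseline as a modelled visit, it averages in a sample taken before treatment, when no arm difference is expected, and is diluted.

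**5. Populations.** The safety population needs only one leukapheresis or one enzalutamide dose and is analysed as treated. The immune response population needs 3 infusions and at least 10 weeks of enzalutamide. The same variables cannot have both as their stated analysis set without one being named the main one. Protocol 8.3 sends only safety variables to the safety population.

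**The case against.** The strongest reply is that little turns on the label. The protocol's designation is unambiguous, one SAP sentence departs from it, and both measures are analysed whatever the label. SAP 4 declares all analyses descriptive or exploratory because of the reduced sample size. All of this stands, and it limits the harm to labelling. But exploratory status does not say which endpoint is primary, and the report must still name one.

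It can also be said that SAP 3.2.1 is not a direct conflict, because SAP 4.1 runs the CD54 comparison in the immune response population too. That is fair, and the conflict there is by implication. Yet SAP 4.1 files CD54 under product characterization, and the immune response list in SAP 4.2 does not include it.

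Several stronger readings are tempting and are not supported:

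- **That the sponsor switched the primary endpoint.** No available text records a switch, and SAP 2.1 still states the PA2024 objective. The SAP text ahead of section 1 was not available, so this holds only for what could be read.
- **That SAP 1 also declares CD54 primary.** It states a design aim only.
- **That the PA2024 analysis was dropped.** SAP 4.2 specifies it and SAP 5 lists proliferation tables.
- **That the proliferation table titles show a wrong population.** SAP 5 says titles may change and that a separate report plan governs content.
- **That a definite amount of power is lost.** SAP 4.2 names visit-specific contrasts, which a baseline visit does not dilute. A figure for the arm effect would describe an analysis that the SAP does not specify.

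**Conclusion.** SAP 4.1 is wrong as written and must be corrected. One sentence calls CD54 primary and one design phrase leans the same way. Protocol 2.1, 8.4.1 and 8.5.3 and SAP 2.1 say otherwise directly, and SAP 3.1 and 3.2.1 do so by implication. SAP 3.2.3 contradicts SAP 3.2.1 on the population, and SAP 4.2 leaves out the rule that names the main comparison.

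The size is a mislabelled primary result, not a lost analysis or a quantified loss of power or error control. The conclusion rests on the wording of the two documents; the power check shows only that the stated design figures belong to T cell proliferation.

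**What to change.** In the SAP:

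- **4.1 and 1:** delete the sentence that makes CD54 primary and the CD54 design phrase.
- **4.2:** state that the log PA2024 stimulation index is the primary endpoint, analysed in the immune response population.
- **3.2.3:** remove immune response variables from the safety-population sentence.
- **4.2:** restore the Protocol 8.5.3 rule: the arm effect, unless the treatment-by-visit interaction has p<0.05, then by-visit contrasts. Take the arm effect over post-baseline visits. Protocol 8.5.3 does not say whether baseline is a modelled visit, so this needs stating. List the visits that count, including whether the post-treatment 100 mL sample in Protocol Table 1 is one of them; SAP 1 does not list it.
- **4.1:** keep cumulative CD54 as an other analysis with one test. The protocol's log-scale t-test and the SAP's Wilcoxon test must be reconciled.
- **4:** keep the statement that all results are exploratory.

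The cost is SAP wording, with no new data.

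If CD54 was truly intended as primary, SAP wording is not enough. Protocol 2.1, 8.2, 8.4.1 and 8.5.3 would have to be amended with a dated rationale, and SAP 2.1, 3.1 and 3.2.1 brought into line.
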